7.3.2. VAS Score for Pain

The VAS pain score will be summarized with descriptive statistics by visit and treatment group. In addition, the changes from baseline will be summarized. Furthermore, the proportion of patients with a VAS pain score >0 mm or ≥ 40 mm will be tabulated by visit and treatment group.

7.3.3. Additional Local Safety Measures.

Local safety expressed by erythema edema and draize scores as well as assessment of nodules and hematomas (number and severity) will be listed but not summarized.

7.3.4. Adverse Events

Adverse events will be coded using MedDRA. Adverse events will be grouped by SOC and preferred term (PT). Only treatment emergent adverse events will be summarized. Treatment Emergent Adverse Events (TEAEs) are defined as all AEs that start (or worsen) on or after the start of first study drug administration in this study and before the start of the optional treatment extension. It is assumed that AEs that started in study ND0612H-006 will not be recorded on the case report form of the present study (unless the event in question worsened during the present study), as these events will not be TEAEs in the present study. For patients who do not participate in the optional treatment extension, events that start >28 days after the last dose of study medication will not be defined as TEAEs. The summary tables will present the frequency and percentage of total subjects and number of events, by SOC and by PT.

For tables of incidence of AEs, subjects who experience the same AE (in terms of the MedDRA PT) more than once will only be counted once for that event in the number of subjects but all occurrences of the same event will be counted in the number of events.

Events with a missing start time, but with a start date equal to the date of first dose of study treatment after baseline will be considered treatment-emergent. If the AE start date is incomplete, it will be imputed as follows for the purpose of determining TEAE:

- If the start date is completely missing, the start date will be equal to the date of the first dose of study treatment. However, if the stop date is not missing and is before the date of the first dose of study treatment, then the stop date will be used instead.
- If the start day is missing, but the month and year are not missing and are equal to the month and year of the first study dose, then this event will be considered as TEAE.
- If the start day and month are missing, then the first day of the first month (January) will be used.

The original date and time will be shown on all listings of AEs. Listings will be provided for all AEs, serious AEs, AEs leading to study treatment discontinuation, AEs leading to dose adjustment/temporary withdrawal and deaths.

The following summaries will be provided:

- A table of the overall incidence (number and percentage) of patients reporting TEAEs and the number of TEAE events and event rates adjusted to exposure, drug-related TEAEs, severe TEAEs, serious TEAEs, TEAEs leading to study treatment discontinuation, TEAEs leading to dose adjustment/temporary withdrawal, and TEAEs leading to death
- TEAEs by SOC and PT, both as number of events, event rates adjusted to exposure and patient counts and percentages
- TEAEs by PT, both as number of events, event rate adjusted to exposure, patient counts, sorted by descending frequency of patients reporting TEAEs in Regimens 1
- Drug-related TEAEs by PT, both as event, event rate adjusted to exposure and patient counts and percentages
- Severe TEAEs by PT, both as event, event rate adjusted to exposure and patient counts and percentages

- Drug-related TEAEs by SOC, PT and severity both, as event, event rate adjusted to exposure and patient counts and percentages
- Serious TEAEs by PT, both as event, event rate adjusted to exposure and patient counts and percentages
- TEAEs leading to study treatment discontinuation, both as event, event rate adjusted to exposure and patient counts and percentages
- TEAEs leading to dose adjustment/temporary withdrawal, both as event, event rate adjusted to exposure and patient counts and percentages
- TEAEs classified by SOC, PT and the time of onset both as event, event rate adjusted to exposure and patient counts and percentages. For this summary, the time of onset will be classified as <7 days, 7-30 days or >30 days

In addition, the following analyses will be performed for the most common or relevant TEAEs (at least for the 10 most commonly reported PTs in both regimens 1 and 3 including also dyskinesia in case it is not among the 10 most common ones):

- The time to first onset of each TEAE within each treatment group will be summarized with Kaplan-Meier methods. In these analyses, the patients who did not experience the AE in question will be censored at the time of the last visit. Separate Kaplan-Meier plots (including separate curve for each treatment group) will be done for each PT.

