All safety data will be summarized using either summary statistics or frequency tabulations, as appropriate to the type of data. Adverse events will be coded using Medical Dictionary for Regulatory Activities (MedDRA). Adverse events will be grouped by system organ class (SOC) and preferred term (PT) and summarized as described above. Only treatment emergent AEs will be summarized. Treatment emergent AEs (TEAEs) are defined as all AEs that start or worsen on or after the start of first study drug administration in the present study and before the start of the optional treatment extension (for the 1 year analysis). For patients who do not participate in the optional treatment extension, events that start >28 days after the last dose of study medication will not be defined as TEAEs. In addition to the frequency counts and percentages, the TEAEs will be presented as annualized rates. The annualized rates will be calculated by the total number of reported AEs divided by the total exposure time measured as the total subject years of exposure to the study medication.

Primary safety analyses will be based on TEAEs with a focus on AESI, i.e., infusion site reactions, hypersensitivity and polyneuropathy. Summaries of total number of cases will be presented as number of events, event rates adjusted to exposure and patient counts and percentages. For hypersensitivity and polyneuropathy, summaries will be broken down by outcomes (unknown, recovered, not yet recovered, recovered with sequelae and death); time to onset will be presented by Kaplan Meier figures, and with descriptive statistics. The Visual Analogue Scale (VAS) pain score will be summarized with descriptive statistics by visit and treatment group, changes from baseline will be summarized and the proportion of patients with a VAS pain score >0 mm or \geq 40 mm will be tabulated by visit and treatment group.

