Additional safety visits will be scheduled for all subjects 2 and 3 months after the last study dose. This will be Month 14 and Month 15 for subjects with treatment up to Month 12 who chose not to continue to the optional treatment extension period. For subjects stopping treatment at Month 36 after the optional treatment extension, such visits will be scheduled at Month 38 and Month 39. For subjects stopping treatment at Month 102 after the optional long-term treatment extension period, such visits will be performed at Month 104 and Month 105. In case of early termination, these visits will be performed 2 and 3 months after early termination.

Assessments will be limited to:

• Urine pregnancy test for female subjects of childbearing potential if required by local legislation.

• Infusion site assessments will be performed and infusion site reactions will be reported as AESI (see Section 10.1.3)

9.2.6 Optional Treatment Extension Period (Visits Months 15, 18, 21, 24, 27, 30, 33, 36)

Subjects will be allowed to continue with study treatment for an optional treatment extension period of 24 more months in which clinic visits will be performed every 3 months.

Assessments will be limited to:

- Urine pregnancy tests for female subjects of childbearing potential will be performed at all clinic visits. The site will provide the subject with monthly home urine pregnancy kits. The subject will perform these tests at home on a monthly basis, and the site will contact the subject by phone and report the results of the monthly home tests on the source documentation.
- Vital signs (including supine [after resting for at least 5 min] and standing BP, pulse rate, and body temperature)
- Infusion site assessments will be performed and infusion site reactions will be reported as AESI (see Section 10.1.3)
- Blood test for vitamin B6, vitamin B12 and folate (Months 18, 24, 30, 36 only)
- Recording of AEs including SAEs and AESIs
- Home diary "ON/OFF" diary entries will be reviewed for completeness and accuracy
- New home "ON/OFF" diary will be dispensed (at Months 15, 21, 27, and 33 only). New pump diary will be dispensed at every extension period visit (Months 15, 18, 21, 24, 27, 30, and 33).
- Concomitant medication review (including anti-PD medication).
- Subjects will be provided with infusion sets, syringes and study medication sufficient for 1 month

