- Unrelated: Adverse event judged by the investigator as NOT having a reasonable suspected causal relationship to the investigational medicinal product

Action Taken

The investigator will describe the action taken in the appropriate section of the eCRF, as follows:

Action Taken:

- None
- Study Drug Stopped
- Study Drug temporarily interrupted
- Concomitant medication
- Other

Action Taken with Study Treatment:

- Dose Increased
- Dose Not Changed
- Dose Reduced
- Drug Interrupted
- Drug Withdrawn
- Not Applicable
- Unknown

Recording and Follow-up of Adverse Events

Adverse events will be recorded from informed consent to the final safety follow-up visit or the Early termination visit (if applicable). Subjects should be followed up for 3 months after receiving the last dose of study drug, and any AEs that occur during this time should be reported according to the procedures outlined above.

The subject will be followed as part of this protocol for 3 months after the last dosing.

All investigators should follow up subjects with AEs until the event is resolved or until, in the opinion of the investigator, the event is stabilized or determined to be chronic.

Documentation and Reporting of Adverse Events

AEs should be reported and documented in accordance with the procedures outlined below. All AEs occurring during the study must be documented on the relevant eCRF pages. The following data should be documented for each AE:

- Description of the symptom event
- Classification of "serious" or "not serious"
- Severity
- Date of first occurrence and date of resolution (if applicable)
- Action taken
- Causal relationship
- Outcome of event (unknown, recovered, not yet recovered, recovered with sequelae, death [with date and cause reported])

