11.1.4 Primary Analyses

11.1.4.1 Methods of Analysis

Adverse events will be coded using the Medical Dictionary for Regulatory Activities (MedDRA). Adverse events will be grouped by system organ class (SOC) and preferred term (PT) and summarized by treatment regimen. Only treatment emergent AEs (TEAEs) will be summarized. TEAEs are defined as all AEs that start or worsen on or after the start of first study drug administration in the present study and before the start of the optional treatment extension (for the 1-year analysis). It is assumed that AEs that started in study ND0612H-006 will not be recorded on the case report form of the present study (unless the event in question worsened during the present study), as these

events will not be TEAEs in the present study. For subjects who do not participate in the optional treatment extension, events that start >28 days after the last dose of study medication will not be defined as TEAEs.

The summary tables will present the frequency and percentage of total subjects and number of events, by SOC and by PT.

For the summaries of AEs, subjects who experience the same AE (in terms of the MedDRA PT) more than once will only be counted once for that event in the number of subjects but all occurrences of the same event will be counted in the number of events. In addition, separate summaries will be provided for AEs by severity and relationship to study drug, as well as separate summaries for AEs leading to study drug discontinuation and SAEs.

In addition to the frequency counts and percentages, the AEs will be presented as annualized rates. The annualized rates will be calculated by the total number of reported AEs divided by the total exposure time, measured as the total subject years of exposure to the study medication.

The below listed summaries will be produced for the Safety Set. In general, all safety endpoints will be summarized using either summary statistics or frequency tabulations, as applicable to the type of data.

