5.4. Handling Withdrawals and Missing Data

In general, there will be no imputation for missing data, unless otherwise specified

The primary objective of this study is safety. Safety data will not be subject to any imputation and will be summarized on an observed case basis. For the analysis of the AEs, the incomplete follow-up will be taken into account by summarizing the data as annualized rates in addition to the

frequency counts and percentages. The analysis of the annualized rates takes into account the actual duration of the exposure to the study treatment.

For the efficacy endpoint, the missing data will be handled as follows:

- For patients who withdraw from the study, data at the early termination visit will be excluded from the by-visit summaries but will be included in the closest visit in case this visit was missing.
- For the continuous efficacy endpoints, likelihood-based modeling approach will be used to handle incomplete data. For this purpose, Mixed Model for Repeated Measures (MMRM) will be applied, see section 8.2.1.
- For categorical efficacy endpoints, the last non missing available data will be used for incomplete data.

All withdrawals will be included in all analyses up to the time of withdrawal. Subjects who are withdrawn prematurely from study drug and/or the study will be included in all analyses regardless of the duration of treatment.

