7.2. Study Drug Administration

Duration of treatment (days treated) is the number of days on treatment based on the first and last days of treatment with the study drug (last day of study drug – first day of study drug + 1).

The following information will be summarized by treatment regimen and overall.

- The number of patients exposed to study treatment
- Mean Duration of exposure (days)

- Total exposure to study treatment, expressed as person years (sum of exposure to study treatment over all patients, classified by treatment regimen)
- Number of patients who reduced ND0612 dose and the mean reduction from baseline to each visit

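### Exposure-adjusted TEAE rates count events to 28 days after last dose but person-time only to last dose; the Kaplan-Meier censoring date and late-onset infusion-site reactions are not tied to that window either

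*SAP*

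**What the plan says.** **Event window.** SAP 7.3.4 restricts the summaries: "Only treatment emergent adverse events will be summarized". For patients not entering the extension, "events that start >28 days after the last dose of study medication will not be defined as TEAEs". The Protocol Synopsis puts the adverse events of special interest (AESI) on the same footing: "Primary safety analyses will be based on TEAEs with a focus on AESI".

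**Rate denominator.** Protocol 11.1.4.1 defines the annualized rate as the number of events "divided by the total exposure time, measured as the total subject years of exposure to the study medication". SAP 5.4 agrees: "The analysis of the annualized rates takes into account the actual duration of the exposure to the study treatment". SAP 7.2 calculates duration of treatment "based on the first and last days of treatment with the study drug", with no post-treatment days added.

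**Kaplan-Meier censoring.** SAP 7.3.1.2 (hypersensitivity), 7.3.1.3 (polyneuropathy) and 7.3.4 (commonest preferred terms) censor event-free patients at their last visit. The SAP does not say which visit that is. No curve is planned for infusion-site reactions as a group.

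**Collection after stopping.** Protocol 10.1.1 follows subjects for 3 months after last dose, and "any AEs that occur during this time should be reported according to the procedures outlined above". Protocol 9.2.5 limits follow-up visits 2 and 3 to a pregnancy test where local law requires one and an inspection of the infusion sites. The instruction has the same words as in 9.2.4 for visit 1: "Infusion site assessments will be performed and infusion site reactions will be reported as AESI (see Section 10.1.3".

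**The concern.** A rate needs events and time at risk from the same interval. Here an event 20 days after last dose enters the numerator, but those 20 days never enter the denominator. The Kaplan-Meier curves may err in the other direction. If the last visit is the 3-month follow-up, a patient who stopped stays in the risk set after day 28, when no event can be counted.

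There is also a gap between collection and reporting. Two visits are held almost entirely to look at infusion sites, yet a reaction that begins after day 28 enters no table. This is a safety study with AESIs as its primary endpoint and local tolerability as its stated focus. Event counts, rates and onset curves are its main product.

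**Working it through.** The documents state no event rate, dropout figure or extension uptake, so there is no plan figure to reproduce. The windows come from the text; everything marked as assumed does not.

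**1. Windows set side by side (patients not entering the extension)**

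| Quantity | Ends, relative to last dose |
|---|---|
| TEAE count (SAP 7.3.4) | day 28 |
| Rate person-time (SAP 7.2) | day 0 |
| At-risk time, if last visit is the last treatment visit | about day 0 |
| At-risk time, if last visit is follow-up visit 1 (four weeks, ±3 days) | about day 28 |
| At-risk time, if last visit is follow-up visit 3 (3 months, ±5 days) | about day 91 |
| Infusion-site inspection (Protocol 9.2.5) | about day 91 |

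The stretch with collection but no summary is 91 − 28 = 63 days, or 63/91 = 69% of post-treatment follow-up.

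**2. Rates**

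Assumed: a share *d* of patients drop out, evenly over 365 days; a share *u* of completers enter the extension; everyone else is observed to day 28 after last dose; *f* is the hazard after stopping divided by the hazard on treatment.

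- Share not entering the extension: s = d + (1 − d)(1 − u)
- Mean exposure per patient: 365(1 − d/2) days
- Relative overstatement: f × 28 × s / [365(1 − d/2)]

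| d, u | s | Mean days | f = 0 | f = 0.5 | f = 1 |
|---|---|---|---|---|---|
| 10%, 90% | 0.10 + 0.90 × 0.10 = 0.19 | 346.75 | 0% | 0.77% | 28 × 0.19/346.75 = 1.53% |
| 30%, 70% | 0.30 + 0.70 × 0.30 = 0.51 | 310.25 | 0% | 2.30% | 28 × 0.51/310.25 = 4.60% |
| 50%, 50% | 0.50 + 0.50 × 0.50 = 0.75 | 273.75 | 0% | 3.84% | 28 × 0.75/273.75 = 7.67% |

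**3. Kaplan-Meier curves**

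Assumed: true 12-month incidence p; constant hazard h = −ln(1 − p)/365 through last dose + 28 days; nothing countable after that; event-free dropouts censored at last dose + c days. In large samples the 12-month estimate is 1 − exp(−∫ e(t)/a(t) dt). Here a(t) is the share at risk and e(t) the rate of countable events. With c = 28 the ratio is h throughout and the true value is returned. With c = 91, dropouts in days 29 to 91 add to a(t) but not to e(t).

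| p = 10% | d = 10% | d = 30% | d = 50% |
|---|---|---|---|
| Follow-up visit 3 (c = 91) | 9.86% | 9.54% | 9.15% |
| Follow-up visit 1 (c = 28) | 10.0% | 10.0% | 10.0% |
| Last treatment visit (c = 0), tail events counted | 10.07% | 10.25% | 10.49% |

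The first row requires every event-free dropout to attend visit 3. The last row falls back to 10.0% if no events follow stopping. For scale, the standard error at 10% with 210 patients is √(0.10 × 0.90/210) = 2.07 percentage points.

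**4. Late infusion-site reactions**

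On the same assumptions, 210 × 0.19 = 40 to 210 × 0.75 = 158 patients would pass through days 29 to 91 off treatment if all stayed in follow-up. The documents give no late-onset rate, so this cannot be turned into a number of reactions.

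**The case against.** The strongest reply is that the 28-day cut-off is a deliberate rule. It is the same in the Protocol Synopsis, Protocol 11.1.4.1 and SAP 7.3.4, and it matches follow-up visit 1 and the SAE reporting period. The primary objective concerns the 12-month treatment period, and all AEs are listed, so nothing is lost. Any rate error overstates harm. The Kaplan-Meier shift is well inside one standard error. All of this stands, and it limits the point to alignment and one table.

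A reader might also infer more than the documents support:

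- **That reactions found at visits 2 and 3 are excluded.** The cut-off is on onset. A reaction that began by day 28 counts whichever visit finds it.
- **That the SAP says outright that late reactions are only listed.** This follows from reading SAP 7.3.4 with the Synopsis. SAP 7.3.1.1 speaks of total infusion-site reactions without restricting them to TEAEs.
- **That the rate rule is left open.** Numerator and denominator are both fixed; they simply do not match. Only the Kaplan-Meier date is undefined.
- **That rates are badly inflated.** For one patient who stops at 90 days the mismatch is 28/90 = 31.1%, but the planned rates pool events and person-time. The pooled 7.7% needs 50% dropout, 50% uptake and an unchanged hazard. An unchanged hazard is hard to credit for infusion-site reactions once infusion has ended.
- **That the data cut-off is contradictory.** Protocol 11.1 (data up to Month 12), Protocol 11.1.6 (available follow-up data included) and SAP 1.1 (timing of the analysis) can be read together. Detail is missing, but there is no conflict.

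**Conclusion.** The rate window is wrong as written. For patients not entering the extension, events count to last dose + 28 days over person-time that ends at last dose. The overstatement runs from 0% to at most about 1.5-7.7%, with the upper figures resting on the assumed dropout and uptake and on a hazard that does not fall after stopping. Patient counts and percentages are unaffected.

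The Kaplan-Meier censoring date needs a definition. The shift is slightly downward under the follow-up visit 3 reading, nil under follow-up visit 1, and nil to slightly upward under the last treatment visit.

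The missing table of late-onset infusion-site reactions is a cheap improvement rather than an error. Overall the effects are modest and no hypothesis test depends on them, but the changes are worth making before database lock.

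**What to change.** Keep the 28-day TEAE definition and amend the SAP as follows.

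1. End person-time for TEAE rates at the earliest of last dose + 28 days, start of the extension, and last contact. This matches the event window and the counts shown in the same tables. Restricting rates to on-treatment events would instead separate them from those counts.
2. Censor the TEAE Kaplan-Meier analyses at that same date in place of the undefined last visit.
3. Add one summary table of infusion-site reactions with onset more than 28 days after last dose, up to the last safety follow-up visit.

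The cost is SAP wording and one more table, with no new data. Rates will change slightly and will average over the 28-day tail. If no events occur there, they fall below the on-treatment rate by 28s/(mean days + 28s): 5.32/352.07 = 1.5% to 21/294.75 = 7.1% under the same assumptions. A footnote stating the window deals with this.

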9.1 Pre-treatment

9.1.1 Screening Visit (for Cohort 2 only; up to 40 days before Day 1)

Subjects in Cohort 1 do not need to repeat screening procedures.

Before performing any study activity, the subject will be thoroughly informed on all aspects of the study. The subject will be requested to sign an EC/IRB approved ICF, after which a screening number will be assigned to the subject. The consent process for this study will include a video demonstration of the handling of the drug-pump system to aid in the subject's consideration of this aspect of the study.

Subjects will be assessed for study eligibility by the investigator at the screening visit(s). Screening procedures can be performed over several days. The maximal interval between the screening and baseline visits is 40 days. The following screening procedures will be performed:

- Informed consent
- Review of inclusion/exclusion criteria (including MMSE assessment and modified Hoehn & Yahr staging; see Appendices 17.1 and 17.2, respectively)
- Demographic data collection.
- Complete medical history, including disease history
- Review of prior and concomitant medication review (including anti-PD medication)
- Urine pregnancy test for female subjects of childbearing potential
- Vital signs (including supine [after resting for at least 5 min] and standing blood pressure (BP), pulse rate, and body temperature
- Body weight and height
- 12-lead ECG recording (single). In the event of possible ECG findings by the central ECG assessor, additional ECG reads could be added at follow-up visits as deemed necessary.
- Safety laboratory tests, including blood chemistry, hematology, serology, and dipstick urinalysis (see Section 10.1.2 for details)

- Physical and neurological examination
- Assessment of suicidality using C-SSRS (see Section 10.1.8 and Appendix 17.3)
- Assessment of impulsive-compulsive disorders in PD using the QUIP-RS (see Section 10.1.10 and Appendix 17.4)
- Recording of AEs (starting from signing of the ICF).
- Dispense home "ON/OFF " diary (see Section 10.2.1.1 and Appendix 17.12)
- Training of subjects and study partners on motor state assessment and recording using the home "ON/OFF" diary
- Dispense pre-programmed, locked pump for training purposes.

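### SAP 7.3.4 counts an adverse event with a missing start day in the month of first dose as treatment-emergent even when its stop date shows it ended before first dose (minor)

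*SAP*

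**What the plan says.** SAP 7.3.4 defines treatment-emergent adverse events (TEAEs) by timing: they "are defined as all AEs that start (or worsen) on or after the start of first study drug administration in this study". Only TEAEs are summarised. Three bullets then deal with incomplete start dates, for the purpose of deciding TEAE status:

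- **Start date wholly missing.** The start is set to first dose. However, "if the stop date is not missing and is before the date of the first dose of study treatment", the stop date is used instead, and the event falls before treatment.
- **Day missing, month and year known.** If these equal "the month and year of the first study dose, then this event will be considered as TEAE". No exception follows.
- **Day and month missing.** "If the start day and month are missing, then the first day of the first month (January) will be used".

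On collection, Protocol 10.1.1 states "Adverse events will be recorded from informed consent to the final safety follow-up visit", and it requires a resolution date, where applicable, for each event. For Cohort 2, Protocol 9.1.1 adds: "The maximal interval between the screening and baseline visits is 40 days". SAP 3.1 gives 28 days for the same interval. Protocol 11.1.4.1, which describes the adverse event analysis, contains no imputation rule.

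**The concern.** The first bullet accepts a stop date as proof that an event was over before treatment began. The second bullet ignores the same proof. A record with more information about its onset therefore gets a worse classification than one with no onset information at all, and the result conflicts with the definition at the head of the section.

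Adverse events are the primary endpoint, and all the summaries are built on TEAEs. Each misclassified event adds one to the numerator of an exposure-adjusted rate without changing the denominator. It may also add a subject to a percentage. The study has no untreated arm in which the same error would occur and cancel.

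**Working it through.** The plan gives no figure to reproduce. The check applies the rules as written to test records and then looks at how large the exposed window is.

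**1. Can such a record exist?** Yes, in Cohort 2. Collection starts at consent, dosing can follow up to 40 days later, and the resolution date is a required item. Cohort 1 has no screening period and consents at Day 1 (Protocol 9.1.1 and 9.2.1), so it has essentially no pre-dose window.

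**2. Rules applied to test records.** First dose is assumed to be 20 June 2017.

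| Start date recorded | Stop date | As written | With a stop-date exception in bullet 2 |
|---|---|---|---|
| 5 June 2017 | 10 June | not TEAE | not TEAE |
| wholly missing | 10 June | not TEAE | not TEAE |
| 2017 only | 10 June | not TEAE | not TEAE |
| June 2017, day missing | 10 June | **TEAE** | not TEAE |
| June 2017, day missing | 25 June | TEAE | TEAE |
| June 2017, day missing | none | TEAE | TEAE |

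An event that ended 20 − 10 = 10 days before dosing is excluded at every level of date completeness except one. The exception changes that row only.

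**3. Length of the exposed window.** The rule applies only to days in the calendar month of first dose that precede first dose. With first-dose dates spread evenly over 2017 (assumption), a day count gives an average of 14.7 such days:

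- 40-day window: 14.7 / 40 = 37% of it.
- 28-day window: 14.7 / 28 = 52% of it.

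**4. Rough size.** Three assumptions are needed, none from the documents: adverse events are reported evenly over time, treatment lasts 365 days, and 1% to 3% of events lack a start day. Then

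share of events exposed = exposed days / (screening days + treatment days) × proportion lacking a start day

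- 15 / (40 + 365) = 15 / 405 = 3.7%
- 3.7% × 1% = 0.037%, about one event in 2,700
- 3.7% × 3% = 0.11%, about one event in 900

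Under these assumptions the shares are ceilings, because the event must also have stopped before first dose. Five exposed events would need between 5 × 900 = 4,500 and 5 × 2,700 = 13,500 recorded events. More frequent reporting on infusion than in screening would lower the share, and early discontinuation would raise it. The documents give no adverse event total, so this does not convert into a count.

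**The case against.** **Counting uncertain dates as treatment-emergent is the usual cautious default.** That is right when the stop date is missing or falls on or after first dose, and the default should stay. It does not cover a stop date before first dose, because the timing is then no longer uncertain. The first bullet already concedes this, and the rule for a wholly missing medication start date in SAP 6.5.2 makes the same check.

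**The general TEAE definition could be read as overriding the bullet.** The bullet is a specific, unconditional instruction, and a programmer would code it as such.

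**The event may have worsened on treatment.** Protocol 10.1.1 requires a change in severity to be recorded as a separate event, so a record that closed before first dose cannot be one that worsened afterwards.

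**Such records will be rare.** This stands. Protocol 12.3 provides for queries on missing or inconsistent data. Screening is short and includes at least four home training sessions, so recall is recent. An exact stop date alongside an unknown start day in the same month is an unusual combination. These points reduce the number of cases but do not repair the rule.

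**The consequences are limited.** This also largely stands. The error can only overcount, so it cannot hide harm. An event that was over before dosing would be expected to be judged unrelated and so stay out of the drug-related tables. It should not be recorded as a reason for stopping treatment, so the tolerability percentages should not move. A subject count for a preferred term changes only if that subject has no other TEAE with the same term. The listings show the dates as recorded, so any case can be seen.

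**Conclusion.** Wrong as written, minor. The second bullet of SAP 7.3.4 contradicts both the SAP's own TEAE definition and the exception in its first bullet, and nothing else in the documents corrects it. The effect is an overcount of TEAEs, essentially in Cohort 2, probably of zero to a few events. That size is a judgement resting on the assumptions above, since the number cannot be derived from the documents.

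A reader might infer more than this. Four stronger readings are not supported:

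- *Screening events in general enter the TEAE tables.* They do not. The error needs a missing start day, onset in the calendar month of first dose, and a known stop date before first dose.
- *The primary safety results are materially inflated.* Nothing in the documents shows this, and the rough calculation points the other way.
- *The miscounted events could not be due to ND0612.* They could not be due to ND0612 given in this study, but Cohort 2 admits subjects who completed an earlier ND0612 study.
- *The rule breaks the time-to-onset analyses.* The bullets are limited to deciding TEAE status. How partial dates enter the onset categories and Kaplan-Meier curves is a wider and separate matter.

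**What to change.** Add one clause to the second bullet of SAP 7.3.4: *unless the stop date is known and precedes first dose in this study, in which case the event is not treatment-emergent*. Leave the rest of the rule unchanged. Here a known stop date means a complete one. If the stop day is also missing within that month, the order is still uncertain and the event stays a TEAE.

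The change should not go on to set the remaining partial-date events to the date of first dose. That would place them all on Day 1, load the earliest onset category and the start of the Kaplan-Meier curves, and amount to a new analysis choice.

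The cost is one clause in the SAP and one condition in the derivation program. No data collection or protocol change is needed.
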